### 4.2.2 Subject Recruitment

Subjects with pain following a knee replacement surgery will be recruited by the investigators, following all HIPAA guidelines, to ascertain their level of interest and willingness to take part in this project.

### 4.2.3 Duration of Subject Participation

Each subject's participation will last approximately 13 months (Group #1) or approximately 16 months (Group #2, if the subject chooses to crossover).

### 4.2.4 Duration of Study

### 4.2.5 Subject Disposition

Subjects that meet all eligibility criteria, including persistent average baseline pain scores of ≥ , will be enrolled in the study and randomized to either Group #1 or Group #2.

### 4.2.6 Vulnerable Population

Vulnerable populations, such as prisoners, employees that report to investigators, or children, are excluded from participation in this study and will not be enrolled.

### 4.3 Sample Size and Justification

Up to 15 sites will participate in this study. Up to individuals will be enrolled as subjects and randomized to either Group #1 or Group #2. Subjects will be randomized at the start of Visit 2, after final eligibility is verified and before lead placement procedures begin.

Subjects who sign an informed

consent form and do not meet all study eligibility criteria will be considered screen failures and not count against the number of enrolled subjects.

4.4 Study Endpoints	4.4	Study	Endp	oints
---------------------	-----	-------	------	-------

Outcome measures will be collected from each subject in Group #1 (8 weeks of active stimulation) and Group #2 (8 weeks of sham stimulation) at Baseline and at specified follow-up visits

To support the study endpoints, the following outcome measures will be used:

- 1. Brief Pain Inventory, Short Form (BPI-SF)
- 2. Diary
  - Average affected Knee Pain (rated using BPI Question 5)
  - Medication affecting pain, including reason for use
- 3. Western Ontario McMaster Universities Osteoarthritis Index (WOMAC)
- 4. Patient Global Impression of Change (PGIC)
- 5. Pain Catastrophizing Scale (PCS)
- 6. 6 Minute Walk Test (6MWT)

### 4.4.1 Primary Endpoints

### 4.4.1.1 Primary Efficacy Endpoint

The primary efficacy endpoint will be average post-operative pain, for primary TKR subjects only, in the affected knee from weeks 5-8 of the treatment period (in both Group #1 and Group #2) compared to baseline.

All subjects will record average knee pain scores (BPI-SF Question #5) for the affected knee in diaries Subjects will record one pain score per day. For each subject, the 7-day baseline diary collection period will be used to calculate the mean of the "average pain." Each randomized subject must obtain ≥ 50% reduction during weeks 5-8 of the treatment period relative to the baseline score to be considered a success.

The primary endpoint of the study compares the proportion of successes of Group #1 (Treatment) relative to that of Group #2 (Control),

### 4.4.1.2 Primary Safety Endpoint

[figure not shown]
The primary safety endpoint is the occurrence and type of study-related adverse events, also known as adverse device effects (ADEs). All ADEs that occur during the study will be documented and analyzed.

### 4.4.2 Secondary Endpoints

Secondary endpoints will be collected to evaluate what effect, if any, the interventions have on each measure. Changes from baseline will be evaluated as secondary efficacy endpoints for the following outcome measures:

- Durability of the treatment effect on average pain intensity
- Average pain over the past week (BPI-5)
- o Pain medication usage
- Pain Catastrophizing Scale (PCS)
- Patient Global Impression of Change (PGIC)
- o Pain Interference (BPI-9)
- Western Ontario McMaster Universities Osteoarthritis Index (WOMAC)
- 6 minute walk test (6MWT)

### 4.5 Amending the Protocol

This study will be carried out in accordance with this Study Protocol. SPR Therapeutics will prepare written amendments to revise the protocol, if necessary. Changes that are deemed administrative in nature, which do not require IRB approval (such as editorial changes for clarity or changes to contact information) may be made without any further approval. Documentation of the approval of the amendment will be maintained in the study regulatory files.

### 5.0 Study Procedures

[figure not shown]
The study procedures for this protocol are classified according to the following time periods: Baseline, Lead Placement, Treatment, and Follow-up. During the 8-week treatment period, Group #1 will receive active stimulation while Group #2 will receive sham stimulation. Following the follow up visit, Group #2 will choose to participate in an optional cross over and receive active stimulation or be

[figure not shown]
discharged from the study. Throughout the study, subjects will be asked to rate their average pain intensity over the last 24 hours in a daily diary and over the last week using the BPI-5. Medication usage and adverse events will be recorded.

### 5.1 Visit 1: Baseline

Individuals that have undergone a knee replacement surgery and report average post-surgical pain intensity over the past week rated as ≥ (BPI-5) will be considered for enrollment into the study. Individuals will receive a detailed explanation of study-specific procedures as well as the risks and benefits of participating in the study. The individual will be asked to sign the approved study consent during this visit. If the individual agrees to participate by signing the consent form, general inclusion/exclusion criteria will be verified, and baseline information will be collected and recorded. Subject ID will be assigned.

### 5.2 Visit 2: Lead Placement and Testing (Day 0)

Following the baseline visit, individuals who qualify for lead placement (i.e., meet the additional inclusion and exclusion criteria) will return to the clinic for placement of the percutaneous leads.

[figure not shown]
# 5.2.1 Randomization Qualifying individuals will be randomized to either Group #1 (Treatment) or Group #2 (Control) using block randomization Individuals will be blinded to their randomization assignment.

[figure not shown]
randomized will be considered enrolled in the study.

[figure not shown]
The group to which each subject is randomly assigned will remain concealed from the subject and the blinded evaluator until after Visit 11, but the randomization assignment will be made known to the unblinded study staff. The randomization assignment may be revealed early if considered medically necessary by the investigator.

[figure not shown]
# After randomization assignment, subjects will be prepared for the lead placement procedure, which is identical for both groups except for use of active stimulation.

[figure not shown]

[figure not shown]
Group #1: Stimulus parameters will be adjusted

Group #2: The procedure will be identical to Group #1 except that no active stimulation will be delivered.

### 5.2.6 Treatment period or Subject Disposition

At the end of Visit 2 (and Visit C1 for Group #2 cross-over subjects), there are three options:

### 5.2.9 Telephone Follow-up

All subjects will receive a Telephone Follow-up 24 - 48 hours after lead placement to query for any adverse device effects (ADE). All ADEs will be followed until resolution.

### 5.3 Visit 3 – 1 Week Post Lead Placement

Subjects will return approximately 1 week after the start of treatment.

### 5.4 Visit 4 – 2 Weeks Post Lead Placement

[figure not shown]
The subject will return approximately 2 weeks after the start of treatment.

### 5.5 Visit 5 - 3 Weeks Post Lead Placement Phone Call

[figure not shown]
The subject will receive a Telephone Follow Up from the unblinded evaluator approximately 3 weeks after the start of treatment

5.6 Visit 6 – 4 Weeks Post Lead Placement  The subject will return approximately 4 weeks after the start of treatment lead placement
5.7 Visit 7 – 5 Weeks Post Lead Placement Phone Call  The subject will receive a Telephone Follow Up from the unblinded evaluator approximately 5 weeks after the start of treatment
5.8 Visit 8 – 6 Weeks Post Lead Placement  The subject will return approximately 6 weeks after the start of treatment lead placement.
5.9 Visit 9 – 7 Weeks Post Lead Placement Phone Call  The subject will receive a Telephone Follow Up from the unblinded evaluator approximately 7 weeks after the start of treatment
5.10 Visit 10 – 8 Weeks Post Lead Placement: lead removal and end of treatment (EOT)
The subject will return approximately 8 weeks after the initial lead placement.

the leads will be removed for both groups, marking

5.13 Visit C1: Crossover Lead Placement, Group #2 Visit C1 is similar to the lead placement at Visit 2.
Leads will be placed
The stimulation parameters will be set
For Group #2 subjects who received leads at this visit, the options for subject disposition will be the same as at Visit 2
Subjects will receive a Telephone Follow-up 24 - 48 hours after each Visit C1 (Lead Placement for Group 2 subjects that crossover) to query for any adverse device effects (ADE). All ADEs will be followed until resolution.
5.14 Visit C2 – 2 Weeks Post Lead Placement, Group #2 Subjects will return approximately 2 weeks after the start of crossover treatment (SOCT).

### 5.15 Visit C3 – 4 Weeks Post Lead Placement, Group #2

The subject will return approximately 4 weeks after the start of crossover treatment.

### 5.16 Visit C4 – 8 Weeks Post Lead Placement, Group #2

The subject will return approximately 8 weeks after the start of crossover treatment.

### 5.17 Follow-up Phone Call visits for Group #2:

Visit C5 (3 months after start of crossover treatment [SOCT]),

Visit C6 (6 months after SOCT),

Visit C7 (9 months after SOCT),

Visit C8 (12 months after SOCT)

Group #2 subjects that crossed over and completed a treatment period with the therapy (Visits C1-C4) subject will receive a Telephone Follow Up approximately 3, 6, 9, and 12 months after the start of crossover treatment

[figure not shown]
### 5.19 Study Visit Windows

The acceptable windows for each visit are listed in Table 4. The study visit windows in Table 4 are guidelines, but every effort should be made to collect all study data, even if out of window.

Table 4 Study Visit Windows

Visit Number	Visit Name	Window
n/a	Consent	
1	Baseline	
2	Lead Placement (SOT)	
2.1	Follow-up call	
3	1 week Stimulation	
4	2 week Stimulation	
5	3 week Stimulation call	
6	4 week Stimulation	

7	5 week Stimulation call	
8	6 week Stimulation	
9	7 week Stimulation call	
10	8 week Stimulation	
11	3 month follow-up	
	Group #	1 Follow Up:
12	6 months follow-up call	
13	9 months follow-up call	
14	12 month follow-up call	
	Group #2 Cro	ssover/Follow Up:
C1	Crossover lead placement (SOCT)	
C1.1	Follow-up call	
C2	2 week Stimulation	
C3	4 week Stimulation	
C4	8 week Stimulation	
C5	3 month follow-up call	
C6	6 month follow-up call	
C7	9 month follow-up call	
C8	12 month follow-up call	

5.21 Subject Compensation

Individuals will receive compensation for full participation in all study visits to cover expenses while taking part in this study.

All Group #1 and Group #2 subjects will receive:

- after the completion of Visit 1
- after the completion of Visit 2 Screening
- after the completion of Visit 2 Testing
- after the completion of each Visit 3, 4, 6, 8, 10, and 11
- after the completion of each Visit 5, 7, and 9 phone calls

Group #1 subjects will also receive:

after the completion of each Visit 12-14

Group #2 subjects that crossover to receive stimulation will also receive:

- after the completion of Visit C1 Testing
- after the completion of each Visit C2-C4
- after the completion of each Visit C5-C8 phone calls

If a subject volunteers to participate in an additional Visit 2 (returns for another session of stimulation testing or lead replacement) the subject will receive compensation at the completion of that visit.

If a subject participates in an Unscheduled Visit (other than an additional Visit 2), they will receive compensation for completion of that unscheduled visit.

#### **6.0 Informed Consent Process**

In accordance with applicable regulations, it is the responsibility of the Principal Investigator to give each participant full and adequate verbal and written information about the objectives of the study, the study procedures, and the potential risks of participating in the study prior to inclusion in the study.

# 7.0 Data Collection and Management

#### 7.1 Data Collection

[figure not shown]
For this study, an Electronic Data Capture (EDC) system which utilizes electronic CRFs (eCRFs) will be used. A 21 CFR Part 11 compliant system will be selected for use which enables entry of study data into an Electronic Data Capture system by each participating clinical site. The EDC system will be validated prior to being available for data entry at the sites and will include appropriate electronic security measures such as controlled password protected access, storage and back-up on the data on a secure HTTP (SSL) server, and appropriate data entry logic and validation checks.

Paper source documents, where applicable, will be completed and maintained in a fashion that is consistent with accepted Good Clinical Practices. If necessary, corrections to the source documentation will be made by using a single line strikeout with the initials and date of the person making the correction. The corrections will be made so as not to obscure the original data. Correction fluid or correction tape may not be used. Where specified, the Principal Investigator must sign and date the source documentation and questionnaires.

All paper study documentation will be stored in a locked storage facility (either a locked office or a locked cabinet). After subject randomization and through Visit 11, surveys will be administered by a study team member who will not know the randomization assignment of each subject and thus will be designated as a Blinded Evaluator.

### 7.2 Confidentiality of data

Every effort will be made to protect subject confidentiality. Subject names and personal identifiers will not appear in any publications resulting from this work.

### 7.3 Data processing

SPR Therapeutics, Inc. (or their authorized representatives) will be responsible for database creation, generation of database queries, and data analysis.

[figure not shown]
7.4 Subject Screening and Identification Log A subject screening log will be completed at the clinical site for all subjects who were considered for the study.
7.5 Subject numbering Screened and consented consecutive subjects will be given a unique Subject ID number. Subjects who sign consent and do not meet all study eligibility criteria will be considered screen failures and not count against the number of enrolled subjects. Subjects who are randomized will be counted as enrolled.
7.6 Blinding  Blinding  of subjects will not be broken until the subject completes Visit 11 and completes the pain/medication diary, unless necessary for medical reasons and the safety of the subjects
Each site will designate a study team member to serve as the blinded evaluator, who will not know the randomization assignment of the subjects.
Unblinded study staff will perform all activities that cannot be performed by the blinded evaluator.

[figure not shown]
SPR Therapeutics, Inc.

8.0 DATA ANALYSIS AND STATISTICAL METHODS

All primary and secondary outcome data will be analyzed and reported.

CONFIDENTIAL Page 39 of 63

### 8.3 Safety Endpoint Analysis

All study-related adverse events will be documented, reported, and categorized.

[figure not shown]
# 9.0 Study Training, Monitoring, and Device Accountability

# 9.1 Study Training

SPR Therapeutics or their designee will conduct a Site Initiation and Training Visit prior to initiation of the study. The purpose of this visit will be to develop a common understanding of the clinical protocol, Case Report Forms (CRFs), study specific procedures, Investigator Responsibilities, and Good Clinical Practices (GCPs) among the clinical research monitors and the Study Team at each Site.

### 9.2 Study Monitoring

SPR Therapeutics or a designated qualified study monitor will monitor this study. Other appropriately qualified clinical monitors may also be involved in the monitoring of study sites. Monitoring visits to the Clinical Site will be conducted periodically, as determined by the rate of subject enrollment, during the study to ensure that the most currently approved version of the Protocol is being followed and that the site is in adherence with all Good Clinical Practices and any specific study Data Monitoring Plan that is in place. In addition, source documents will be reviewed for accuracy against data found on the Electronic Data Capture system.

### 9.5 Independent Clinical Events Reviewer

An Independent Clinical Events Reviewer (ICER) will be utilized for this study to adjudicate study related adverse events (AEs). AE information, including group assignment, will be provided to the Reviewer. The adjudication by the Clinical Events Reviewer will be the final determination.

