### 10.0 ADVERSE EVENTS AND UNANTICIPATED ADVERSE DEVICE EFFECTS

An Adverse Event (AE) is defined as any untoward medical occurrence in a patient whether or not related to the medical device or procedure. Adverse Events will not be captured unless they are study related or the relationship is unable to be determined.

An Adverse Device Effect (ADE) is a study-related Adverse Event. Adverse Device Effects (ADEs) that occur during the study will be captured on an Adverse Event Form

and reported to the Sponsor. If the relationship of the adverse event to the System is not able to be determined, it will be captured on an Adverse Event Form and reported to the Sponsor. Specific details regarding the ADE, including the event category, severity of event, and seriousness will be collected. Any necessary treatment or intervention required and the resolution status of the ADE will also be documented. ADEs will be followed to resolution. Any ADEs that meet the requirements for Medical Device Reporting (MDR) will be entered into SPR's complaint system.

All ADE's are further categorized as anticipated or unanticipated. Any ADE's specified in the Risk Analysis of this Study Plan will be considered "anticipated". All other ADE's are considered "unanticipated". Anticipated events that occur with a greater frequency than expected are also considered unanticipated.

An Unanticipated Adverse Device Effect (UADE) is defined as any serious adverse effect on health or safety or any life threatening problem or death caused by, or associated with, a device, if that effect, problem or death was not previously identified in nature, severity or degree of incidence in this Study Plan or application or any other unanticipated serious problem associated with a device that relates to the rights, safety or welfare of subjects.

[figure not shown]

Table 2: Unanticipated Adverse Device Event Sponsor Contact Information

	UNANTICIPATED ADVERSE SPONSOR CONTACT IN	DEVICE EVENT	
Name/Title	Email address	Telephone Number	Fax Number

It is the responsibility of the investigator to inform his/her Institutional Review Board (IRB) of any ADEs and UADEs as required by the IRB. In addition, some IRBs will require that AEs that are serious in nature, even if not study related, will be reported as well. SPR Therapeutics is responsible for furnishing the required information to the appropriate regulatory authorities.

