# 5.2.4 Pain Medication Usage at 4 weeks, 8 weeks, and 3, 6, 9, and 12 months after SOT 1) Pain medication usage between groups

The analysis of pain medication usage examines changes in medication usage between the two groups. Changes in medication will be reviewed for Weeks 1-4 of therapy, Weeks 5-8 of therapy, and at 3, 6, and 12 months after the start of therapy. For this analysis, a blinded third-party medication committee will review medications of study participants collected for each diary collection period and will use the following convention for scoring medication changes, in comparison to the baseline diary medications:

- No change = No change in dosage or change is not clinically meaningful to impact pain outcomes.
- Increase = Clinically meaningful increase in medication that would impact pain outcomes.
- **Decrease** = Clinically meaningful decrease in medication that would impact pain outcomes.

The blinded third-party medication committee (comprised of three clinicians experienced in the treatment and management of pain) will serve as the evaluator for all clinical sites. Final determinations of changes in medication usage will require agreement among at least two of the three blinded evaluators. In cases where there is 1:1:1 tie, the medication review committee will convene to discuss and adjudicate the final determination.

The distribution of changes in opioid pain medication usage (decrease/no change/increase) will be reported first using an exact Mantel-Haenszel test to compare the ordered distributional responses (percentage of subjects within each category) between Group #1 and Group #2. Group #1 at Weeks 1-4, Weeks 5-8, and 3 months will be compared to Group #2 at Weeks 1-4, Weeks 5-8, and 3 months, respectively. Group #1 at 6, 9, and 12 months will be compared to Group #2 at 3 months (the longest follow-up before crossover). Assuming there is a statistically significant difference in the ordered distributional responses between Group #1 and Group #2 at a given timepoint, a subsequent statistical test will be carried out to compare between groups the percent of subjects categorized as having a decrease in opioid pain medication. In addition to opioids, this analysis will also be repeated for analysis of all pain medications, and non-opioid analgesic usage independently.

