### 6.4 Safety Population

The Safety set is based on the Full Analysis Set with the following modifications:

- Subjects will be assessed with an As Treated analysis, with therapeutic group determined by the treatment they actually received.
- Any subjects for whom lead placement is attempted will be included, even if no leads are implanted
- Any subjects for whom treatment is not attempted (*i.e.* no attempted lead placement occurs) will be excluded.

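### The reviewer whose adjudication of study-related adverse events is final is given group assignment, and the plan shows no masked read first

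*Protocol*

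**What the plan says.** Protocol 9.5 assigns the adjudication of study-related adverse events to one Independent Clinical Events Reviewer. On what the Reviewer sees, it says: "AE information, including group assignment, will be provided to the Reviewer". On the standing of the result, it says: "The adjudication by the Clinical Events Reviewer will be the final determination".

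Protocol 4.4.1.2 makes the ADEs, meaning adverse events related to the study, the primary safety endpoint; the Synopsis agrees. SAP 9.1 presents, by treatment group, how many subjects and what percentage had any ADE, a serious one, an unanticipated one, or one leading to death.

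On blinding, Protocol 5.2.1 says that the assignment "will remain concealed from the subject and the blinded evaluator until after Visit 11" and is known to unblinded study staff. Protocol 7.6 follows the same pattern: the subject and one designated evaluator per site are blinded, and other staff do what the evaluator cannot. Neither section mentions the Reviewer.

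**The concern.** Whether an event is related to the study, and what kind of event it is, are matters of judgement. If the person whose judgement is final knows the arm, part of any difference between arms in the ADE table could come from that knowledge and not from the device. The table is the visible output for a primary endpoint in a trial described as double-blinded, and its readers will compare the two columns. As written, the plan would give them no means of telling how far arm knowledge shaped the calls.

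**Working it through.** No arithmetic applies. The documents give no ADE rates and state no figure on this point, so the check sets the passages against each other.

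1. **Is the adjudicated item the endpoint?** Yes. Protocol 10.0 defines an ADE as a study-related adverse event, 4.4.1.2 makes ADEs the primary safety endpoint, and 9.5 sends study-related events to the Reviewer for a final call. That call therefore feeds the table in SAP 9.1.

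2. **Is the arm known when the call is made?** Probably. Protocol 9.5 lists assignment as part of the information supplied and describes no later unmasking step. It does not state the order, so this is an inference, though the natural one.

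3. **Does another passage mask the Reviewer, or say why the arm is supplied?** None that is visible. Protocol 5.2.1 and 7.6 cover the subject and the blinded evaluator only.

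4. **Is the arm needed to put an event in the right column?** No. SAP 6.4 analyses the safety set as treated, "with therapeutic group determined by the treatment they actually received". Grouping is therefore a data step that can follow adjudication.

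5. **Could the arm sway a call?** For some events. The Synopsis has leads placed in all subjects, and of the sham arm the protocol's lead placement text says: "The procedure will be identical to Group #1 except that no active stimulation will be delivered". Lead and procedure events can thus occur in either arm. An event plainly due to the lead or the procedure is study-related in both arms and leaves little room for influence. The exposed events are the ambiguous ones, which might be put down to stimulation, to the lead or to neither. A reviewer who knows that no stimulation was delivered may attribute or categorise such an event differently.

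6. **Could a reader detect this in the data?** Hardly. Protocol 10.0 says: "Adverse Events will not be captured unless they are study related or the relationship is unable to be determined". There is therefore no table of all adverse events, free of a relatedness judgement, to compare with the ADE table.

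7. **For how long could masking work?** Up to Visit 11. After that, Table 4 in Protocol 5.19 shows Visits 12 to 14 for Group #1 only and C1 to C8 for Group #2 only, so the visit itself reveals the arm.

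8. **What analysis is exposed?** A descriptive summary by group. No between-arm safety test is visible, so no type I error rate or power figure is involved. The primary efficacy endpoint comes from subjects' pain diaries and does not pass through this Reviewer.

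**The case against.** The strongest defence is that the arm is real causal information. Sham subjects receive no stimulation, so whether stimulation could have caused an event depends on it, and the UADE definition in Protocol 10.0 turns on the device's part in the harm. This stands. It is a reason to let the Reviewer see the arm at some stage and to let that informed call govern safety reporting. It does not require the arm to be known before any call has been recorded.

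It can also be said that the room for influence is narrow. Lead and procedure events are study-related in both arms, and anticipated status follows largely from whether the event is listed in the Risk Analysis and how often it occurs. Unblinded site staff may also have judged an event before the Reviewer sees it. All of this stands, and it limits the gain.

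Three stronger readings are tempting, and the documents do not support them:

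- **The plan breaches its own blinding.** A reader might infer this from the double-blind label. But 5.2.1 and 7.6 promise concealment only from the subject and the blinded evaluator, and 9.5 discloses the Reviewer's access openly. This is a design choice, not a contradiction.
- **The plan is inconsistent because it masks another outside panel.** SAP 5.2.4 does say that "a blinded third-party medication committee will review medications of study participants collected for each diary collection period". That shows masked outside review is feasible in this trial. But those calls feed a between-group test and concern a different judgement, so they set no rule for safety adjudication.
- **The plan fails to say what is adjudicated.** The visible text does not itemise it, but text around these sections has been withheld, so its absence cannot be counted as a gap.

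**Conclusion.** The point holds as a minor design weakness. As the visible plan reads, a judgement that feeds a primary endpoint, and is final, is open to arm knowledge that could be withheld until a first call is recorded.

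It rests on two inferences: that the arm is available when the call is made, and that adjudication covers attribution or category. Both are natural readings of 9.5, and neither is stated.

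The size cannot be determined. The documents give no event rates and nothing on how often arm knowledge would change a call. The effect could be nil, and it could run either way. A reader might infer that the ADE comparison is biased in favour of the device, or that it is invalid. The documents support neither: they show a possible influence on a descriptive table, with no effect on efficacy.

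**What to change.** **Protocol 9.5.** For events up to Visit 11, have the Reviewer record and lock a masked determination before group assignment, and any stimulation details that reveal it, are released. The Reviewer may then make an unmasked determination where stimulation-specific causality or UADE/MDR assessment needs one. That determination stays final for safety reporting, so 9.5 still yields one final call per event. Where no second look is needed, the masked call is the final one.

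**SAP 9.1.** Present the by-group ADE summary under both the masked and the final determinations. List every call that changed, and mark calls on events after Visit 11 as unmasked. Showing both matters: a table of masked calls alone could carry a superseded determination, and a table of final calls alone would hide any effect of unmasking.

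**Cost.** Someone must redact each review packet and manage the lock, some events get a second look, and the report gains one table and a short listing of changed calls. There is no gain for events after Visit 11, or for any earlier judgement by unblinded site staff.
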